9.2. Plasma concentrations and pharmacokinetic parameters

9.2.1. Plasma PK parameters

Blood samples will be drawn (see section 16.1):

- For cohorts A, B and C:
 - on Day 1 at pre-dose then post-dose (after start of infusion) at H0.5, H1, H1.5, H2, H4, H6, H6.5, H7, H7.5, H8, H10, H12, H16, then at D2 (H24), D3 (H48), D4 (H72) and D5 (H96).
In case of infusion less than 6 hours, blood sample for Ir-CPI pharmacokinetics will be done at the end of infusion then H0.5, H1, H1.5, H2, H4, H6, H10, H18, H42, H66 and H90 after the end of infusion.
- For cohort D:
 - on Day 1 at pre-dose then post-dose (after start of infusion) at H0.5, H1, H1.5, H2, H4, H6, H6.5, H7, H7.5, H8, H10, H12, H16, then at D2 (H24), D3 (H48), D4 (H72), D5 (H96) and D7 (H144).
In case of infusion less than 6 hours, blood sample for Ir-CPI pharmacokinetics will be done at the end of infusion then H0.5, H1, H1.5, H2, H4, H6, H10, H18, H42, H66, H90 and H138 after the end of infusion.

Relevant plasma pharmacokinetic (PK) parameters will be calculated for Ir-CPI by non-compartmental methods, as appropriate for those participants with sufficient plasma concentration data. The rules defined in the previous section (0) will be used.

The different areas under the concentration-time curve (AUC) will be calculated using the linear trapezoidal summation (both the ascending phase and the descending phase).

The following plasma pharmacokinetic parameters will be calculated for Ir-CPI:

Parameters (unit)	Definition
C_{\max} (ng.mL)	Maximum observed plasma concentration
t_{\max} (h)	Time to reach maximum observed plasma concentration
AUC_{0-6h} (ng/mL.h)	Area under the plasma concentration-time curve from time zero to 6 hours
AUC_{0-last} (ng/mL.h)	Area under the plasma concentration-time curve from time zero to the last measurable plasma concentration

Parameters (unit)	Definition
AUC_{0-96h} (ng/mL.h)	Area under the plasma concentration-time curve from time zero to 96 hours (in order to be comparable between all the 4 cohorts)
AUC_{0-144h} (ng/mL.h)	Area under the plasma concentration-time curve from time zero to 144 hours (only for Cohort D)
AUC_{0-inf} (ng/mL.h)	Area under the plasma concentration-time curve from time zero to infinity, calculated as follows: $AUC_{0-inf} = AUC_{0-last} + C_{last}/\lambda_z,$ where C_{last} is the last quantifiable concentration
$t_{1/2}$ (h)	Terminal elimination half-life, calculated as follows: $t_{1/2} = \text{Ln}(2)/\lambda_z$
λ_z (h^{-1})	Terminal elimination rate constant
CL (L/h)	Total body clearance, calculated as follows: $CL = \text{Dose} / AUC_{0-inf}$
Vd_z (L)	Volume of distribution, calculated as follows: $Vd_z = CL / \lambda_z$

9.2.2. Plasma pharmacokinetic analysis

The plasma pharmacokinetic analysis will be performed on the PKS set.

Subjects receiving placebo will not be included in the summary and analysis of PK parameters. Listings with plasma concentrations (including dates and times of PK blood sampling) and PK parameters will be provided by treatment group and subject. These listings will be generated for all subjects with an available PK profile (complete or incomplete), including those who are excluded from the PKS.

Plasma concentrations and PK parameters of Ir-CPI including descriptive statistics will be presented in tables separately for each treatment group.

Individual plasma concentration versus time profiles of Ir-CPI will be presented graphically on linear and log/linear coordinates for each subject.

The graph of arithmetic mean \pm SEM over time will be provided for plasma concentration of Ir-CPI on linear and log/linear coordinates with all treatment groups (cohorts A, B, C and D) on the same graph. A reference line corresponding to the lowest C_{max} values at the NOAEL (No Observed Adverse Effect Level), i.e. 53.7 μ g/mL will be added on the graph of mean and individual concentration-time profiles on log/linear coordinated only.

A graph of arithmetic mean \pm SEM with min-max curves over time will be provided for plasma concentration of Ir-CPI for each treatment group on linear coordinates.

Individual plasma concentration-time profiles (spaghetti plots) of Ir-CPI will also be presented for each treatment group on linear coordinates.

Box whisker plots will be generated for the comparison of C_{max} , AUC_{0-6h} , AUC_{0-96h} , AUC_{0-last} and AUC_{0-inf} .

The linear dose-proportionality of the maximum concentration (C_{max}) and the areas under the concentration-time curve (AUC_{0-6h} , AUC_{0-96h} , AUC_{0-last} and AUC_{0-inf}) will be assessed for Ir-CPI using an exponential regression model ("power model") that measures the degree of non-linear proportionality [2]. The PK parameter and dose values will be logarithmically

transformed prior to analysis and evaluated using a 1-factor analysis of variance (ANOVA) including log (dose) as fixed effect and subject as random effect.

Linear dose-proportionality will be concluded if the two-sided 90 % confidence interval (CI) for the slope value of the log-transformed dose is within the critical $[(1+\ln(LL)/\ln(r)) ; (1+\ln(UL)/\ln(r))]$ region, where $r = \text{Dose Maximum/Dose Minimum}$, $LL = 0.8$ and $UL = 1.25$ [2].

The following SAS® code will be used:

```
proc mixed data=ADPP method=REML;
  by PARAMCD;
  class USUBJID;
  model ln(AVAL) = ln(dose) / solution cl alpha=0.10 ddfm=kr;
  random USUBJID;
run;
```

10. Pharmacodynamics data

The pharmacodynamic analysis will be performed on the PDS set.

PD aPTT, Factor XI and Factor XII inhibition will be measured by the change from baseline (central lab). PD aPTT and FXI/FXII parameters will be measured (see section 16.1):

- For cohorts A, B and C:
 - on D1, pre-dose then at 30min, 60min, 90min, 2h, 4h, 6h, 6h30, 7h, 7h30, 8h, 10h, 12h, 16h post-dose, then on D2 (24h), D3 (48h), D4 (72h), D5 (96h) and discharge visit (D10 ± 2 days) (see section 16.1).
In case of infusion less than 6 hours and besides assessment at pre-dose, 30 min, 60 min, 90 min, 2h and 4h after start of infusion, parameters should be measured at the end of infusion, then 30min, 60 min, 90min, 2h, 4h, 6h, 10h, then 18h, 42h, 66h and 90h after the end of infusion and then at the discharge visit.
- For cohort D:
 - on D1, pre-dose then at 30min, 60min, 90min, 2h, 4h, 6h, 6h30, 7h, 7h30, 8h, 10h, 12h, 16h post-dose, then on D2 (24h), D3 (48h), D4 (72h), D5 (96h), D7 (144h) and discharge visit (D10 ± 2 days) (see section 16.1).
In case of infusion less than 6 hours and besides assessment at pre-dose, 30 min, 60 min, 90 min, 2h and 4h after start of infusion, parameters should be measured at the end of infusion, then 30min, 60min, 90min, 2h, 4h, 6h, 10h, then 18h, 42h, 66h, 90h and 138h after the end of infusion and then at the discharge visit.

For each time point, including the baseline time point, an aPTT ratio will be calculated by dividing the aPTT value (in sec) of the specific time point (aPTT*) by the baseline aPTT value (in sec) (aPTT°) of the same volunteer (aPTT ratio = aPTT*/aPTT°). The baseline time-point is considered as having an aPTT ratio of 1. A graphical representation of aPTT ratio in function of the time will be done per volunteer. The mean ± SEM, min and max curves will be also represented for each cohort on separate graphs. The mean ± SEM curves of all cohorts (A, B, C, D) will be also represented on one graph.

Concerning FXI and FXII PD parameters, a graphical representation of individual data of FXI activity in each cohort, in function of the time, will be done. Another graphical representation of FXII activity in each cohort, in function of the time, will be done. In these graphs, the normal lower ranges of FXI and FXII activities will be indicated as horizontal lines.

Moreover, FXI or FXII inhibition, expressed in percentages, for each time point (including the baseline time point), has to be calculated for each volunteer. To do so, the calculation is the following:

- Percentage of FXI inhibition= $(100 - ((FXI^*/FXI^\circ) * 100))$
- Percentage of FXII inhibition= $(100 - ((FXII^*/FXII^\circ) * 100))$

FXI* or FXII*: FXI or FXII percentage of inhibition of a specific time point

FXI° or FXII°: FXI or FXII percentage of inhibition of the baseline time point

The baseline time point is considered as 0 % of FXI or FXII inhibition. A graphical representation of FXI or FXII inhibition, expressed as percentages, in function of the time will be done per volunteer. The mean \pm SEM, min and max curves will be also represented for each cohort on separate graphs. The mean \pm SEM curves of all cohorts (A, B, C, D) will be also represented on a same graph.

Descriptive statistics of changes from baseline will be provided by treatment group and each measurement time for changes from baseline of aPTT ratio and absolute values.

Descriptive statistics will be provided by treatment group on each measurement time for aPTT values (absolute values and changes from baseline), aPTT ratio (ratio values and changes from baseline of ratios) and percentage of FXI or FXII inhibition (calculated percentages and changes from baseline of percentages).

All pharmacodynamics parameters will be listed.

11. Exploratory Pharmacokinetic / Pharmacodynamic analysis

Evaluation of the relationship between concentrations of Ir-CPI and the PD parameters: the change from baseline in coagulation parameters (i.e. aPTT ratio) defined above, FXI and FXII inhibition will be graphically investigated and displayed. The analysis will be performed on the PDS.

12. Exploratory Biomarkers Evaluation

The exploratory biomarkers evaluation will be performed on the PDS.

The following exploratory outcome measurements are defined:

- In blood: D-dimers, fibrinogen, prothrombin time PT (expressed in seconds and as INR), TNF α , hsCRP, cystatin C (CysC), ADA.
- In urine: Urinary microalbumin, Kidney Injury Molecule (KIM-1), Urinary Neutrophil Gelatinase-Associated Lopocalin (NGAL).

Samples for D-dimers, fibrinogen, PT, hsCRP and TNF α will be collected at pre-dose on D1 and then 2h, 4h, 6h, 8h, 12h post-dose, at 24h (D2), at 48h (D3), at 72h (D4) discharge visit (D10 \pm 2 days) (see section 16.1).

CysC samples will be collected at screening, then from D1 to D4: pre-dose (D1), 24h (D2), 72h postdose (D4), and then at the discharge visit (D10 \pm 2 days) (see section 16.1).

ADA analysis samples will be collected at pre-dose on the day of infusion, at the discharge visit (D10 \pm 2 days), on D30 and on D90. If ADAs are detected in D90 samples, ADA analysis samples will be collected also at D180 (see section 16.1).

Urine collections will be done at these intervals pre-dose, [0-6h], [6-12h] and [12-24h] after start of infusion. Urinary NGAL, microalbuminuria and KIM-1 will be assessed (see section 16.1).

For each parameter, descriptive statistics will be provided by treatment group on absolute values and changes from baseline for each measurement time. Graph over time by treatment group will be also produced.

Presence of ADA (and their titration for ADA+ samples) and sub-classes determination (isotype) will be described by treatment group and measurement time.

All exploratory parameters will be listed.

13. Safety data

The safety analyses will be performed on the SS.

13.1. Adverse events

Adverse events, including pre-treatment events, will be recorded from the time of consent through the end of the study.

Adverse events will be coded according to MedDRA Version 22.0.

A treatment-emergent adverse event (TEAE) is an adverse event that occurs after IMP dosing or that was present prior to dosing but was exacerbated between dosing during a treatment period and the end of the study.

Adverse events (including AESIs) will be summarised in tables as follows [overall and by System Organ Class (SOC) and Preferred Term (PT)]:

- Number and percentage of subjects with at least one adverse event and number of occurrences of an adverse event by treatment group and overall,
- Number and percentage of subjects with at least one TEAE and number of occurrences of a TEAE by treatment group and overall,
- By intensity, with the number and percentage of subjects with at least one TEAE and number of occurrences of a TEAE by treatment group and overall,
- By causality, with the number and percentage of subjects with at least one TEAE and number of occurrences of a TEAE by treatment group and overall.

If there are only a few adverse events (≤ 10), only a listing will be generated.

All adverse events reported in the Case Report Form (CRF) will be listed with the SOC, the PT and the Investigator's verbatim. All TEAEs will also be listed with the SOC and the PT. An additional listing will be provided for AEs leading to death and other serious and significant AEs (SAEs or AEs leading to study withdrawal).

Note: In case of a change of intensity or causality for an event during the treatment period, the intensity will be the highest recorded intensity and the causality will be the highest likelihood recorded.

13.2. Clinical laboratory data

The following clinical laboratory parameters will be measured at screening, then from D1 to D4: pre-dose (D1), 24h (D2), 72h post-dose (D4), and then at the discharge visit (D10 ± 2 days) (see section 16.1).

Haematology parameters will be listed and grouped as follows:

- Red blood cells: erythrocytes ($10^{12}/L$), haematocrit (ratio), hemoglobin (g/L);
- White blood cells: basophils ($10^9/L$), basophils/leukocytes (%), eosinophils ($10^9/L$), eosinophils/leukocytes (%), leukocytes ($10^9/L$), lymphocytes ($10^9/L$), lymphocytes/leukocytes (%), monocytes ($10^9/L$), monocytes/leukocytes (%), neutrophils ($10^9/L$) and neutrophils/leukocytes (%);
- Other parameters: platelets ($10^9/L$).

Coagulation parameters will be listed and grouped as follows:

- Coagulation parameters: activated Partial Thromboplastin Time (sec) and aPTT ratio (see calculation in section 10).

Blood chemistry parameters will be listed and grouped as follows:

- Liver function: alanine aminotransferase (ALT) (IU/L), alkaline phosphatase (IU/L), aspartate aminotransferase (AST) (IU/L), total bilirubin (fraction of direct bilirubin in case > 1.25 x ULN) ($\mu\text{mol}/L$) and gamma glutamyl transferase (GGT) (IU/L), lactate dehydrogenase (LDH) (IU/L);
- Renal chemistry: creatinine ($\mu\text{mol}/L$) and urea (mmol/L);
- Electrolytes: bicarbonate, calcium, chloride, phosphorus, potassium and sodium (all electrolytes expressed in mmol/L);
- Metabolism parameters: fasting glucose (mmol/L);
- Other proteins: albumin (g/L), creatine kinase (and fraction of CK-MB if > 1.5 x ULN) (IU/L) and total protein (g/L).

Urinalysis parameters will be listed and grouped as follows:

- Planned urinalysis parameters: cylinders, erythrocytes and leucocytes.

For haematology, blood chemistry and coagulation, absolute values and changes from baseline will be described by treatment group (and overall) and measurement time.

For urinalysis, absolute values will be described by summary statistics or frequency tables by treatment group and measurement time.

For haematology, blood chemistry, coagulation and urinalysis, values higher or lower than the laboratory reference range (H, L) will be listed.

For haematology and blood chemistry, a summary table with the number and percentage of subjects with potentially clinically significant abnormal (PCSA) values (defined in section 16.2) will be generated by treatment group (and overall) and measurement time.

For haematology and blood chemistry, shift tables with the number of subjects having values lower than the lower PCSA limit (Low), normal and higher than the upper PCSA limit (High)

(defined in section 16.2) according to the baseline position will be prepared by treatment group and measurement time.

A specific listing of subjects with PCSA values will be generated.

Values (absolute values and changes from baseline) will be listed and data out of normal/PCSA ranges will be flagged with clinical significance information.

Urinalysis values will be listed.

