A pivotal GLP toxicity study in monkey was then designed to support the FIH clinical trial design, by mimicking as much as possible the route and type of administration foreseen, by testing an appropriate safety margin (3, 10 and 30-fold) in regards to the first human clinical dose and by choosing a continuous infusion duration largely exceeding the one foreseen in the FIH clinical trial (i.e. 6 hours). This toxicity study was performed with Ir-CPI administered by continuous IV infusion during 24 h at 3 dose levels (mid, high, super high) with systemic exposure to Ir-CPI up to at least 30-fold the expected therapeutic concentration in humans. The 24 h infusion was followed by a recovery period (24 h or 14 days) at high and

super high doses. No clinical signs or macroscopic findings were observed, except an increase in kidney weight in males at the super high dose (2/3 animals). Microscopic examination showed adverse toxicity (kidneys) in both females and males only at the super high dose in the early scheduled euthanasia animals (24h after ending infusion). Immunohistochemical staining suggested that there was no formation of immune complexes (high or super high doses tested), either for the early or late scheduled euthanasia, suggesting a direct effect of Ir-CPI at the highest dose in the renal tissue. No effect related to ADAs was observed, even though ADAs were detected 9 (one animal) or 11 (all animals) days after ending infusion in the high and super high dose groups. A loss of proportionality in Ir-CPI plasma concentration was observed between the high and the super high dose. During post-infusion, a decrease of Ir-CPI clearance was only observed at the super high dose with a possible link to renal toxicity. Considering these results, the NOAEL was set at 201.6 mg/kg/day. This NOAEL was used to define the MRSD for the FIH clinical study.

Note that in all toxicity studies, a dose-related moderate (rats, monkeys) to marked (monkeys) and reversible prolongation in aPTT was observed in all animals and at all dose levels, showing that Ir-CPI was present and under an active form.

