6.5. Baseline definition

For all parameters, baseline will be defined as the last available measurement prior to the IMP administration.

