- See laboratory safety parameter assessments (section 9.7.6) for list of tests to be run.
- See laboratory safety parameter assessments (section 9.7.6) for list of tests to be run.
- Physical Examination (including basic neurological testing for isocoria, light reflexes, gait and balance) should be performed at screening, on D-1, then 24h postdose (D2) and at the discharge visit.
- An abbreviated physical exam should be performed at 8h postdose on D1.
- Supine vital signs should be measured after 5 minutes of rest in a supine position and include body temperature, resting pulse rate, and blood pressure: at screening, then from D1 to D4, vital signs should be done predose, 60min, 2h, 4h, 6h, 8h, 10h, 12h, 24h, 48h, 72h postdose, and then at the discharge visit (D10+/-2d).
- Cardiac monitoring using telemetry (3-lead minimum and including SpO₂) is to be performed from 1h predose up to 12h postdose.
- ECG should be done at screening, then on D1 (predose, 2h, 4h, 6h, 8h, 12h), 24h (D2), 48h (D3), 72h (D4) postdose and at the discharge visit. Timing can be adjusted based on emerging PK data.

11. See laboratory safety parameter assessments for list of tests to be run (section 9.7.6): screening, then from D1 to D4: Predose (D1), 24h (D2), 72h postdose (D4), and then at the discharge visit.
12. Participants will be asked at baseline if they have been previously exposed to tick bites. At the discharge and extra-ambulatory visits performed for ADA analysis, the participants will be asked if they have been exposed to tick bite since the previous visit (response recorded as yes/no/unknown). If the answer is yes, then the participant will be asked to provide information on treatment (e.g. antibiotics) and on presence of erythema migrans and other signs or symptoms.
13. The baseline chemistry (predose sample) will also contain an extra archive serum sample for anti-Borrelia serology testing (IgG and IgM) as backup to test for anti-Borrelia antibodies due to previous exposure via potential tick bites.
14. Safety aPTT (local lab) at screening, then on D1, predose, then 2h, 4h, 6h, 8h, 12h, D2 (24h), D3 (48h) and D4 (72h) postdose and at the discharge visit.
15. Urinalysis at screening, then predose (D1), 24h (D2), 72h postdose (D4) and at the discharge visit. See laboratory safety parameter assessments for list of tests to be run (section 9.7.6).

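### Urine sediment is the only laboratory panel with no within-subject summary against predose, so new findings not recorded as adverse events are not counted by treatment group

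*SAP*

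**What the plan says.** SAP section 13.2 names the urine items: "Planned urinalysis parameters: cylinders, erythrocytes and leucocytes". Their group summary is one sentence: "For urinalysis, absolute values will be described by summary statistics or frequency tables by treatment group and measurement time". The individual data are also presented: "Urinalysis values will be listed", and out-of-range results are listed as well. Appendix 4 of the SAP has two urinalysis outputs in its section 14 (14.3.3.4.1, summary statistics, and 14.3.3.4.2, a listing of abnormal values) and one full data listing (16.2.8.4).

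The other panels are treated differently in the same section: "For haematology, blood chemistry and coagulation, absolute values and changes from baseline will be described by treatment group (and overall) and measurement time". Two of them go further: "For haematology and blood chemistry, shift tables with the number of subjects having values lower than the lower PCSA limit", with the matching normal and high categories, set against each participant's baseline position.

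A baseline exists for urine too. The schedule for Cohorts A to C (SAP 16.1.1, footnote 15) reads "Urinalysis at screening, then predose (D1), 24h (D2), 72h postdose (D4) and at the discharge visit", and Cohort D has the same times (SAP 16.1.2, footnote 16). SAP section 6.5 states "For all parameters, baseline will be defined as the last available measurement prior to the IMP administration". The urinalysis summary does not use that definition.

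**The concern.** Safety and tolerability are the primary objective. The product inhibits the intrinsic coagulation pathway, and sediment microscopy is the only planned test for red cells and casts in urine. Protocol section 3.2 also reports a renal finding in the 24-hour monkey infusion study: "Microscopic examination showed adverse toxicity (kidneys) in both females and males only at the super high dose". A reader of the safety tables will want to know how many men in each dose group had a sediment abnormality after dosing that they did not have before.

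A frequency at each visit does not answer that. It says how many men are abnormal at 24 h, but not whether they are the same men who were abnormal predose. Predose abnormality is possible under the plan: inclusion criterion 3 accepts isolated out-of-range values that the investigator considers unimportant, and the schedule (footnote 2) does not require the Day 1 predose results before dosing. In groups of six, one or two men with a pre-existing finding could mask a new case in the table or be taken for one.

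**Working it through.** No sample size, power or alpha figure is involved, and the plan states no number to reproduce. The check has two parts: what each panel receives, and what can be deduced from the planned urine outputs.

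**Step 1. Planned summaries (SAP 13.2 and Appendix 4)**

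| Panel | Change from baseline | Table of potentially clinically significant values | Shift table |
|---|---|---|---|
| Haematology | yes | yes | yes |
| Blood chemistry | yes | yes | yes |
| Coagulation | yes | no | no |
| Urinalysis | no | no | no |

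Urinalysis is the only panel with no comparison within the participant. SAP Appendix 2 sets no limits for sediment items.

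**Step 2. What the group table reveals**

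Inputs: each panel has 6 active and 2 placebo participants (SAP section 4). With four panels this gives 4 × 6 = 24 active and 4 × 2 = 8 pooled placebo, 32 in all.

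Let n be the group size, a the number abnormal predose and b the number abnormal at one post-dose time. Only a and b appear in the table.

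- Fewest new cases: all a men stay abnormal as far as b allows, giving max(0, b − a).
- Most new cases: the b abnormal men are drawn first from the n − a who were normal, giving min(b, n − a).

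Illustrative counts for n = 6 (assumed; the documents give none):

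| a predose | b post-dose | Fewest new | Most new |
|---|---|---|---|
| 0 | 1 | 1 | 1 |
| 1 | 1 | 0 | 1 |
| 1 | 2 | 1 | 2 |
| 2 | 2 | 0 | 2 |
| 3 | 3 | 0 | 3 |

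For a = b = 2 the range is 0 to 2 of 6, or 0 % to 33 % of the dose group. The same counts give the same ranges in the pooled placebo group (n = 8). With a = 0 the table is already exact at that visit.

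**Step 3. What the listings reveal**

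Predose plus three post-dose times (24 h, 72 h, discharge) gives 32 × 4 = 128 values per sediment item if complete. SAP section 6.2 sorts listings by group, participant and time, so each man's predose and later results sit together. Every new finding can be identified by reading them.

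**Step 4. What the adverse event tables capture**

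Appendix 2 of the protocol makes a laboratory abnormality an adverse event only if it is clinically relevant, needs treatment, is serious or changes the participant's schedule. Such events are classed as treatment-emergent against the predose state and summarised by group. New sediment findings outside those criteria are in the listings only.

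**The case against.** A reader might infer that new haematuria or casts cannot be told apart from findings present before dosing. The documents do not support that. Predose is itself a tabulated time, all values are listed by participant and time, and 128 values per item can be read by hand. What is missing is a summary.

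A reader might also infer that the kidney was the target organ in monkeys generally, or that casts and urinary bleeding are the forms in which the main risks were expected to appear. The renal toxicity in the 24-hour monkey study occurred at the super high dose only. The two-week monkey study reported changes in various organs. No section predicts casts, and haematuria is not among the protocol's examples of bleeding events of special interest.

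Further points on the other side:

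- Clinically relevant findings already reach the treatment-emergent and special-interest event outputs. This stands, and it confines the gap to findings that are not recorded as adverse events.
- Renal safety is followed elsewhere. Creatinine and urea get changes from baseline, and so do microalbumin, KIM-1, NGAL and cystatin C. This stands for renal function and injury, but none of these counts red cells or casts. The three urinary markers stop at 24 h, whereas sediment continues to discharge. All four biomarkers are analysed on the Pharmacodynamic set, which requires study completion, and not on the Safety set.
- Protocol section 10.2.10.2 asks only for description by group and time. This stands: the SAP does not depart from the protocol.
- Coagulation has no shift table either. That is correct, but it does get changes from baseline.
- Eligibility excludes clinically significant urinalysis abnormalities, so few men may be abnormal predose. That is plausible, and if none are, the planned table is exact at each visit.

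**Conclusion.** The point holds as a gap in the summary tables. Urine sediment alone among the laboratory panels has no within-subject comparison with predose, and new findings that do not qualify as adverse events are not counted by treatment group. They must be read from listings 14.3.3.4.2 and 16.2.8.4.

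The size depends on how many men are abnormal predose. The documents give no such rate, so no expected number is offered here. With none, nothing is lost at a given visit. With two of six before and two after, the table leaves 0 to 2 new cases open. No data are lost, no protocol requirement is breached and no decision rule depends on this table. It is a low-cost improvement to the primary safety summary, using a method that the SAP already applies to haematology and chemistry, for which listings are also planned.

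**What to change.** Add to SAP section 13.2, and to the outputs under 14.3.3.4, a shift table on the Safety set by treatment group for erythrocytes, leucocytes and cylinders. Classify each result as within or above the laboratory reference range, or as absent or present where no range applies. Show predose against 24 h, 72 h and discharge, and predose against the worst post-dose value. Include a row counting participants with a newly abnormal or worsened result.

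The worst-value comparison is needed because counts at separate visits do not show how many different men were affected. With none abnormal predose and one abnormal at each of the three later times, the number of men could be 1, 2 or 3.

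The cost is one table from data already collected. The sponsor has already extended the SAP through two appendices, so the same route is available. If the table is added after unblinding, label it post hoc.
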